#### **8.2.2.3. Survival Status**

The patient's survival status will be assessed during the study and at the day 28 and day 60 FUV and will be documented in the eCRF. In case the patient has died and the date of death is unknown, the date of the last personal contact should be documented at a minimum.

#### **8.2.2.4. Quality of Life Assessment**

Patients will be assessed for quality of life using the EQ-5D at the day 60 FUV.

#### **8.2.2.5. Clinical Status**

Patient's clinical status will be assessed by the Glasgow Outcome Scale at the day 60 FUV.

### **8.2.3. Safety Assessments**

Safety will be assessed based on the following variables:

- AEs (see Section 8.2.3.1)
- Laboratory safety parameters, including creatinine (see Section 8.2.3.2)
- Vital signs (see Section 8.2.3.3)
- Electrocardiograms (see Section 8.2.3.4)
- Physical examination (see Section 8.2.3.5)

Planned time points for all safety assessments are provided in the SoA (Table 2).

#### **8.2.3.1. Adverse Events Assessments**

Adverse events will be assessed throughout the study as specified in the SoA (Table 2). Adverse event reporting will follow special considerations for the ICU setting as described in Appendix 3.

#### **8.2.3.2. Clinical Safety Laboratory Assessments**

In general, blood samples for safety laboratory analysis and creatinine assessment should be obtained at indicated visit days during routine sampling (one representative value, if taken more than once a day). Additional tests may be performed at any time during the study as determined necessary by the investigator or required by local regulations.

See Appendix 1, Table 4 for the list of clinical laboratory tests to be performed and the SoA (Table 2) for timing and frequency.

In clinical studies conducted in the ICU, deviations in laboratory values are to be expected frequently. Clinical judgement should be applied in determining which deviations should be reported as an AE in the sense of an “untoward medical occurrence” and which deviations should be considered usual and expected findings in this setting.

It must be noted that clinically significant laboratory deterioration as assessed by the investigator with onset before end of treatment must be documented in the respective eCRF section. However, it is preferred to document the condition or disease underlying the aberrant laboratory value (e.g., renal failure rather than hyperkalemia) rather than the laboratory value only.

The investigator will exercise his or her medical and scientific judgment in deciding whether an abnormal laboratory finding or other abnormal assessment is clinically significant, and thus constitutes an AE (see also Section 9 and Appendix 3).

If laboratory values from non-protocol specified laboratory assessments performed at the institution’s local laboratory fulfill the aforementioned criteria for clinical significance, then the results must be recorded in the eCRF.

All protocol-required laboratory assessments, as defined in Appendix 1, Table 4, must be conducted in accordance with the SoA (Table 2). Please note that day 1 safety laboratory assessment, including creatinine assessment, has to be done prior to IMP administration only, if more than 12 h elapsed between the screening assessment and the IMP administration.

Urine analysis and serum or urine samples for pregnancy testing will be collected only at screening/randomization. For details on pregnancy testing, refer to Appendix 4.

### **8.2.3.3. Vital Signs**

Vital signs (core body temperature, heart rate, respiratory rate, blood pressure [diastolic and systolic]) will be assessed at indicated visits at pre-dose within 1h before administration of IMP (one representative measurement closest to IMP administration) and at further time points whenever medically indicated. Blood pressure and heart rate measurements will be assessed with an intra-arterial catheter, or a completely automated device. Manual techniques will be used only if an automated device is not available.

### **8.2.3.4. Electrocardiograms**

12-lead ECG will be obtained as outlined in the SoA (Table 2) using an ECG machine that automatically calculates the heart rate and measures PR, QRS, QT, and QTc intervals.

### **8.2.3.5. Physical Examination**

A physical examination will be conducted at the time of screening/randomization, on day 1 prior to IMP administration only, if more than 24 h elapsed between screening assessment and IMP administration, and on the days of further IMP administration, as specified in the SoA (Table 2).

The physical examination includes, at a minimum, assessments of the skin, cardiovascular, respiratory, gastrointestinal, and neurological systems.

### **8.2.4. Pharmacokinetics/Pharmacodynamics**

PK/PD testing will be done at selected countries/sites. Blood samples will be collected for measurement of plasma IFX-1 concentrations, C5a, and ADAs of IFX-1 within 1h before administration of IMP, as specified in the SoA (Table 2).

Detailed instructions regarding the collection, processing, etc., of samples will follow local regulations and requirements.

## **9. ADVERSE EVENT COLLECTION AND REPORTING**

All AEs, serious and non-serious (see Appendix 3 I for definitions), must be collected, documented, and reported from signature of the informed consent or, where informed consent is deferred, from the documented decision timepoint of the responsible investigator and/or physicians to enroll the patient until the end of treatment (see Section 9.1.1). They will be further followed up until the end of study (see Section 9.1.1.1), however death and related SAEs with onset during the follow-up period and after the end of study will be collected and reported (see Section 9.1.2).

All AEs will be reported to the sponsor by the investigator in the appropriate sections of the eCRF. It will be specified whether the event is serious or not according to the definition of SAE (see Appendix 3 I). In case of an SAE, the SAE report will be processed by the safety vendor

(see Section 9.2.1). The safety vendor for this study is IQVIA Pharmacovigilance. Reporting of AEs will be done according to the specific definitions and instructions for completing the respective sections of the eCRF.

The investigator and any designees are responsible for detecting, documenting, and recording events that meet the definition of an AE and remain responsible for following up AEs, considered related to the IMPs or study procedures (see Section 9.2.2 and Appendix 3 II for details on causality of AEs), or that caused the patient to discontinue study treatment (see 7.2.4 for treatment discontinuation criteria) or the study.

Care will be taken not to introduce bias when detecting AEs. Open-ended and non-leading verbal questioning of the patient is the preferred method to inquire about AE occurrences.

Due to the severity of disease of the patient population entering this study, numerous problems, signs, and symptoms deviating from normal will be seen during the course of the study. These will not necessarily constitute a reportable AE unless they require significant intervention, lead to discontinuation of blinded study drug, or are considered to be of concern in the investigator's clinical judgement. Similarly, it is preferred to receive documentation of the underlying condition rather than the resulting sign (e.g., 'agitation' rather than 'self-extubation').

In clinical studies conducted in the ICU, deviations, e.g., in laboratory values or temporary changes in arterial blood pressure, are to be expected frequently. Clinical judgement should be applied in determining which deviations should be reported as an AE in the sense of an "untoward medical occurrence" and which deviations should be considered usual and expected findings in this setting. It is preferred to document the condition or disease underlying the aberrant laboratory value (e.g., renal failure rather than hyperkalemia) rather than the laboratory value only.

The records will describe (Appendix 3 II) the nature (diagnosis or single syndrome if possible, alternatively signs and symptoms), severity (mild, moderate, severe, life-threatening, fatal), start date and time, stop date and time, actions taken with respect to the IMP, corrective treatment/therapy given, additional investigations performed, outcome, and causality (relationship to study treatment according to the investigator's assessment; see also Section 9.2.2).

The terms 'disease progression', 'progressive disease', or similar, do not constitute an acceptable description of the nature of an AE. For example, if a patient experiences disease progression with hemoptysis leading to hospitalization, the investigator should file an AE and an SAE for the hemoptysis; data related to disease progression should be captured in the disease assessment and response evaluation section of the eCRF.

Any AE not listed as an expected event in the IB or in this protocol will be considered unexpected.

## 9.1. Time Period and Frequency of Collection and Reporting

The following timeframes for reporting apply from signature of the informed consent or, where informed consent is deferred, from the documented decision timepoint of the responsible investigator and/or physicians to enroll the patient, on:

- All AEs, including AESIs and SAEs until 30 days following the last IFX-1 administration must be reported
- All pregnancies until 30 days after the last dose of treatment with IFX-1 must be reported until completion of the pregnancy, as described in Section 9.5.2

Any time outside of the time period specified above, in addition, any study drug-related SAEs brought to the attention of an investigator must be reported immediately to the sponsor.

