### **9.5.2.      Pregnancy Reporting**

If the patient or partner of a patient participating in the study becomes pregnant during treatment or within 30 days after the last dose of treatment with IFX-1, the investigator should report the pregnancy to [QLS\\[contact]](mailto:[contact]) via e-mail within 24 hours of being notified. The safety vendor will then forward the pregnancy reporting form to the investigator for completion. In case that e-mail contact is not possible, the site can provide an initial pregnancy report in the SAE section of the SAE form and transmit this via the SAE FAX line: [contact].

A patient becoming pregnant while on IMP will immediately be discontinued from treatment and the EOT visit will be performed.

The patient or partner should be followed by the investigator until completion of the pregnancy. If the pregnancy ends for any reason before the anticipated date, the investigator should notify the sponsor. At the completion of the pregnancy, the investigator will document the outcome of the pregnancy. If the outcome of the pregnancy meets criteria for immediate classification as an SAE (i.e., postpartum complication, spontaneous abortion, stillbirth, neonatal death, or congenital anomaly), the investigator should follow the procedures for reporting as SAE.

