### Contraception Guidance

#### *Male Patients*

Male patients with female partners of childbearing potential are eligible to participate if they agree to ONE of the following during the study and until 3 months after last dose of IFX-1:

- Are abstinent from penile-vaginal intercourse as their usual and preferred lifestyle (abstinent on a long term and persistent basis) and agree to remain abstinent
- Agree to use a male condom plus partner use of a contraceptive method with a failure rate of <1% per year as described in Table 5 when having penile-vaginal intercourse with a woman of childbearing potential who is not currently pregnant

Men with a pregnant or breastfeeding partner must agree to remain abstinent from penile vaginal intercourse or use a male condom during each episode of penile penetration [during the protocol-defined time frame].

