### *Female Patients*

Female patients of childbearing potential are eligible to participate if they agree to use a highly effective method of contraception (from the day of study medication initiation throughout the study period and up to 3 months for IFX-1 after the last dose of study medication) consistently and correctly as described in Table 5. During the treatment period of the study conception is assumed to be precluded by the severe clinical conditions for included patients and applicability of sexual abstinence as a contraceptive method can be assessed by the investigator in case a patient confirmation cannot be gained.

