**Collection of Pregnancy Information**

*Male Patients with Partners who Become Pregnant*

The investigator will attempt to collect pregnancy information on any male patient's female partner who becomes pregnant while the male patient is in this study. This applies only to male patients who receive IFX-1.

After obtaining the necessary signed informed consent from the pregnant female partner directly, the investigator will record pregnancy information on the appropriate form and submit it to the sponsor within 24 hours of learning of the partner's pregnancy. The female partner will also be followed to determine the outcome of the pregnancy. Information on the status of the mother and child will be forwarded to the sponsor. Generally, the follow-up will be no longer than 6 to 8 weeks following the estimated delivery date. Any termination of the pregnancy will be reported regardless of fetal status (presence or absence of anomalies) or indication for the procedure.

*Female Patients who Become Pregnant*

The investigator will collect pregnancy information on any female patient who becomes pregnant while participating in this study. Information will be recorded on the appropriate form and

submitted to the sponsor within 24 hours of learning of a patient's pregnancy. The patient will be followed at least monthly to determine the outcome of the pregnancy. The investigator will collect follow-up information on the patient and the neonate, and the information will be forwarded to the sponsor. Generally, follow-up will not be required for longer than 6 to 8 weeks beyond the estimated delivery date. Any termination of pregnancy will be reported, regardless of fetal status (presence or absence of anomalies) or indication for the procedure.

While pregnancy itself is not considered to be an AE or SAE, any pregnancy complication or elective termination of a pregnancy will be reported as an AE or SAE. A spontaneous abortion is always considered to be an SAE and will be reported as such. Any post-study pregnancy related SAE considered reasonably related to the IMP by the investigator will be reported to the safety vendor as described in Appendix 3. While the investigator is not obligated to actively seek this information in former study patients, he or she may learn of an SAE through spontaneous reporting.

Any female patient who becomes pregnant while participating in the study will discontinue IMP.

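### Protocol Version 4.0 has two pregnancy-reporting rules that differ in length and in the partners covered, and both end before the 3-month contraception period does

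*Combined protocol and SAP*

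**What the plan says.** All references are to protocol Version 4.0.

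- **Contraception (Appendix 4).** Men: "during the study and until 3 months after last dose of IFX-1". Women: throughout the study and "up to 3 months for IFX-1 after the last dose of study medication". Footnote b of Table 5 repeats the 3-month figure.
- **Reporting window, rule one (Section 9).** Section 9.1: "All pregnancies until 30 days after the last dose of treatment with IFX-1 must be reported". Section 9.5.2 is triggered when a "patient or partner of a patient participating in the study becomes pregnant during treatment or within 30 days after the last dose of treatment", and the sentence goes on to tie that treatment to IFX-1. Pregnancies caught by this rule are followed to completion.
- **Reporting window, rule two (Appendix 4, Collection of Pregnancy Information).** For patients: "The investigator will collect pregnancy information on any female patient who becomes pregnant while participating in this study". For partners: a "female partner who becomes pregnant while the male patient is in this study". Section 5.6.2.2 ends a patient's study at the day 60 contact, or at death, withdrawal or loss to follow-up if earlier.
- **Partner scope.** Section 9.5.2 sets no limit by arm. Appendix 4 does: "This applies only to male patients who receive IFX-1".
- **After the study.** Appendix 4 keeps a narrower duty: "Any post-study pregnancy related SAE considered reasonably related to the IMP by the investigator will be reported to the safety vendor". Sections 9.1 and 9.1.2 likewise keep drug-related SAEs reportable outside the usual period.

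**The concern.** Section 9.5.2 and Appendix 4 both require notification within 24 hours, but they do not agree on when the duty ends. Suppose a patient has the last dose on day 8 and a pregnancy begins on day 50. Section 9 stopped on day 38; Appendix 4 still applies. A site that reads only Section 9 will not report it.

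The partner rule has a separate difficulty. Phase III is double-blind (Section 5.1.2) and code-breaking is confined to emergencies, so a site cannot know which men received IFX-1. Read literally, the Appendix 4 limit cannot be followed.

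Finally, patients are asked to avoid conception for 3 months after the last dose, yet an uneventful pregnancy conceived late in that period falls under neither rule. What is at stake is the completeness and consistency of pregnancy-outcome data.

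**Working it through.** The plan states no figure for this mismatch, so there is nothing to reproduce. The check is calendar arithmetic.

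**Inputs.** Last dose on day d = 1, 2, 4, 8, 15 or 22 (Section 7.2.1.2). Section 9 window ends at d + 30. Appendix 4 window ends at end of study, nominally day 60 (Section 5.6.2.2). Contraception ends 3 months after the last dose, taken as 90 to 92 days.

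**Formulas, for a patient followed to day 60.** Difference between the two rules = 60 − (d + 30). Days of contraception with no pregnancy rule when both are applied = (d + 90 to d + 92) − 60.

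| Last dose, day | Section 9 ends, day | Section 9 ends before Appendix 4 by (days) | Contraception ends, day | Days with no rule |
|---|---|---|---|---|
| 1 | 31 | 29 | 91–93 | 31–33 |
| 2 | 32 | 28 | 92–94 | 32–34 |
| 4 | 34 | 26 | 94–96 | 34–36 |
| 8 | 38 | 22 | 98–100 | 38–40 |
| 15 | 45 | 15 | 105–107 | 45–47 |
| 22 | 52 | 8 | 112–114 | 52–54 |

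As a share of the post-dose contraception period, the uncovered part runs from 31/90 to 33/92 = 34–36% (last dose day 1) up to 52/90 to 54/92 = 58–59% (last dose day 22). A site using Section 9 alone leaves 90 − 30 to 92 − 30 = 60–62 days uncovered, whatever the last dose day.

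**Sensitivity.** If 60 days after randomization is counted as day 61, the difference between the rules becomes 9 to 30 days.

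**Early end of study.** With last dose on day 8 and withdrawal on day 10, Appendix 4 ends on day 10 and Section 9 on day 38. The difference is 28 days in the opposite direction.

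**Residual drug.** Section 3.2.5 gives a half-life of 3 to 4 days. The fraction of the last dose remaining after t days is 0.5^(t/h), with h = 3 to 4:

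- t = 30 (Section 9 limit): 0.10–0.55%.
- t = 60 − 22 = 38 (day 60, last dose day 22): 0.015–0.14%.
- t = 60 − 1 = 59 (day 60, last dose day 1): 0.0001–0.004%.

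**The case against.** The case for leaving the text alone has four parts.

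1. *Contraception may outlast reporting by design.* This stands. Nothing in the protocol requires the two periods to match, and 30 days is also the general adverse-event window in Section 9.1. A 3-month reporting window is good practice; its absence is not a documented error. The argument does not explain two different reporting windows in the same protocol.

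2. *The windows overlap and do not contradict.* This also stands. Neither rule forbids what the other requires, and a site that always uses the longer one satisfies both. But the protocol does not tell sites to do that, and which window is longer depends on the patient.

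3. *IFX-1 is loosely used for blinded study drug.* Partly right. Sections 5.6.2.2, 9.1 and 9.6 use IFX-1 where both arms must be meant, and Section 9.5.2 also ties its post-treatment window to IFX-1. Reading the Appendix 4 limit as men who received study drug removes most of the partner conflict. That reading should be written down, because the literal one cannot be applied under blinding.

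4. *The important events are already covered.* Largely right. Drug-related SAEs, including pregnancy-related ones, remain reportable after the study. Only uneventful pregnancies, or those with events judged unrelated, fall outside.

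A reader might infer that drug-exposed pregnancies go unmonitored. The documents do not support that: on the stated half-life, at most about 0.14% of the last dose remains at day 60, and Section 5.1 suggests the half-life may be shorter where C5a is very high. The 3-to-4-day value is from single doses in cardiac-surgery patients; no repeat-dose value in COVID-19 is given.

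**Conclusion.** The mismatch is real and minor. Section 9 and Appendix 4 set different windows and different partner scopes. For patients followed to day 60, Section 9 ends 8 to 29 days earlier; that range is not general, since an early end of study can reverse the order. With both rules applied, about 31 to 54 days of the contraception period have no rule for pregnancies as such in patients followed to day 60. These figures rest on a nominal day 60 contact and 3 months taken as 90 to 92 days. The 29-day end needs a patient who stops after one dose and is still followed to day 60. The number of patients affected is not given, and none is assumed.

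It would go too far to say that sites face instructions they cannot jointly obey on timing, or that the protocol breaks a stated requirement by not reporting to 3 months. The one instruction that cannot be applied as literally written is the partner limit by arm. The primary analysis, alpha and power are unaffected.

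**What to change.** 1. State one pregnancy-reporting window in Section 9.1, Section 9.5.2 and Appendix 4. It should be no shorter than the later of 30 days after the last dose and end of study. Preferably it runs to the end of whatever contraception period the sponsor confirms (3 months after the last dose as written), with reporting passive after the day 60 contact and patients told at that contact to notify the site.
2. In Appendix 4, adopt the partner scope of Section 9.5.2, covering the partner of any participating patient.
3. Replace IFX-1 with IMP throughout the pregnancy rules so that they read the same for both blinded arms.

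The cost is amendment wording in three places and, if the longer window is adopted, one line in the day 60 contact script, with no extra visits. The longer window means accepting reports to about day 91 to 114. Its yield will be low, because follow-up is passive and residual exposure on the stated half-life is very small.

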### 9.1.1. During Treatment

All AEs, including SAEs and AESIs, must be collected and reported appropriately from the time of patient/others signing the consent form or, where informed consent is deferred, from the documented decision timepoint of the responsible investigator and/or physicians to enroll the patient until 30 days following the last IFX-1 administration.

- All AEs must be followed until the outcome of the event is ‘recovering’ (for stabilization of chronic conditions), or recovered (/with sequelae), and until all queries related to these AEs have been resolved.
- Ongoing AEs should be reviewed at each scheduled and unscheduled visit until the hospital discharge visit. All details should be recorded in the eCRF. If any AE changes for the worse, in frequency of attacks/symptoms or in severity, a new record of the event must be started (i.e. distinct reports are required for differing frequencies and/or severity of the same event to enable comprehensive safety reports and later analysis).
- If the patient dies from an event, ongoing further AEs can be closed with an outcome ‘unknown’, if outcome was not assessed at day of death.

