## 9.2. Serious Adverse Event Reporting and Timelines

### 9.2.1. Initial Reporting of Serious Adverse Events

SAEs that should be reported within 24 hours on the SAE form are:

- Events with fatal outcome
- New life-threatening events, defined as:
  - Cardiac event requiring CPR or medical resuscitation (adrenaline use etc.) – can be caused by severe arrhythmia or other
  - Life-threatening spontaneous bleeding requiring blood transfusion and / or surgical intervention
  - Thrombo-embolic event with life-threatening hemodynamic or pulmonary instability
  - New life-threatening organ failure / dysfunction
  - Liver: AST, ALT > 20 x upper limit of normal (ULN) OR Bilirubin > 10 x ULN
  - Kidney: Creatinine > 6 x ULN – or newly developed anuria  $\leq$  100 mL urine production over 24h
  - Cardiovascular:
    - Norepinephrine > 1  $\mu$ g/kg/min or equivalent
    - Troponin I: levels consistent with myocardial infarction as defined by manufacturer
  - Coagulation: Thrombocyte count < 20.000 /  $\mu$ L or partial thromboplastin time (PTT) > 2.5 x ULN
  - Life-threatening infections other than COVID-19 which require immediate antibiotic treatment and/or additional medical / surgical intervention
  - Life-threatening infusion reactions which require immediate intensification of existing intensive care treatment, including but not limited to additional vasopressor or fluid support, or high dose corticosteroids and antihistamines

All remaining SAEs should be reported at investigator's earliest convenience. SAEs should be approved by the investigator (see Appendix 3 II). In addition, SAEs need to be reported in the (non-serious) AE section of the eCRF. The investigator will be requested to supply as much detailed information regarding the event as is available at the time of the initial contact.

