#### **10.2.3.4. Safety Analyses**

Safety analyses will be performed based on the SAF.

The occurrence of TEAEs will be compared between treatment arms. TEAEs will be analyzed according to the number and percentage of patients who had a TEAE, as well as the number of TEAEs in total. Additionally, the number and percentage of patients with TEAEs will be further grouped by severity and causal relationship. The number and percentage of patients with serious

TEAEs and AESIs and the number of serious TEAEs and AESIs will be analyzed. Where TEAEs are grouped by severity or relationship, the maximum severity/relationship per patient and class of TEAE will be considered.

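### Each worsening of an AE opens a new record, and nothing links the records of one episode, so the event totals compared between arms can rise with deterioration rather than with the number of events

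*Combined protocol and SAP*

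**What the plan says.** All references are to Protocol V4.0.

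- **Recording.** Section 9.1.1 sets the trigger: "If any AE changes for the worse, in frequency of attacks/symptoms or in severity", then "a new record of the event must be started (i.e. distinct reports are required for differing frequencies and/or severity of the same event". It gives later analysis as one reason for the rule, so these records are meant to reach the analysis data. Section 9 lists five severity levels, from mild to fatal.
- **Comparison.** Section 10.2.3.4 states: "The occurrence of TEAEs will be compared between treatment arms". It reports the patients with a TEAE, "as well as the number of TEAEs in total". For the serious events and those of special interest it plans patient figures, and also "the number of serious TEAEs and AESIs will be analyzed". The synopsis repeats this.
- **Collapsing.** The only rule that reduces several records to one takes the maximum per patient and class. Section 10.2.3.4 applies it where TEAEs are grouped by severity or relationship, and not to the totals.
- **AESIs.** Section 9.6 includes infections other than COVID-19 without a severity threshold.
- **SAEs.** Section 9 requires each AE to be marked serious or not. Section 9.2.1 adds that "SAEs need to be reported in the (non-serious) AE section of the eCRF". Section 9.2.1.1 treats a later change as a follow-up report to the existing SAE.

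**The concern.** A total is useful in a safety comparison if its unit is a distinct event. Here the recording rule splits one clinical course into several records, and the analysis section does not say whether its totals count records or courses. If they count records, a nosocomial pneumonia that goes from moderate to severe to life-threatening adds three to the TEAE total and three to the AESI total, while the same pneumonia that stays moderate adds one to each.

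The extra records follow clinical deterioration, which is also what the efficacy endpoints measure. If IFX-1 works and placebo patients deteriorate more, the placebo AESI total rises without any additional infection. For an agent that blocks a complement mediator, that matters: a higher placebo total could hide an excess of distinct infections on IFX-1. Frequency and severity of TEAEs is also a named secondary endpoint (Section 4.2.2.2).

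**Working it through.** The plan gives no figure for AE counts, so there is none to reproduce. The check has two parts: whether the text leaves the totals exposed, and how large the effect could be.

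**Text.** Section 9.1.1 creates several records for one event. Section 10.2.3.4 totals TEAEs, serious TEAEs and AESIs. The maximum rule is confined to the grouped tables. No section gives an event identifier, a rule for joining records, or a definition of one TEAE. A dataset built from the eCRF without a link can only be summed by record.

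**Size, using the plan's death rates.** Inputs from the plan are 180 patients per arm (90 per arm in each of two stages) and 28-day mortality of 30% on placebo and 15% on IFX-1 (Section 10.2.1). Expected deaths are 180 × 0.30 = 54 and 180 × 0.15 = 27.

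Assumptions not in the documents are:
- m distinct events per patient, equal in both arms, from 1 to 5;
- k extra records for each fatal course, from 1 to 3;
- no extra records for survivors.

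Records are 180m + 27k on IFX-1 and 180m + 54k on placebo.

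| m | k | IFX-1 records | Placebo records | Placebo : IFX-1 |
|---|---|---|---|---|
| 1 | 1 | 207 | 234 | 1.13 |
| 1 | 3 | 261 | 342 | 1.31 |
| 3 | 1 | 567 | 594 | 1.05 |
| 3 | 3 | 621 | 702 | 1.13 |
| 5 | 1 | 927 | 954 | 1.03 |
| 5 | 3 | 981 | 1062 | 1.08 |

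In every row the distinct events are equal, at 180m per arm, so counting linked episodes once gives 1.00.

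**Size, without tying worsening to death.** Let w be the mean number of worsenings per distinct event, again assumed. Records per event are 1 + w, and with equal distinct events the ratio is (1 + w on placebo) / (1 + w on IFX-1).

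- w = 0.1 on IFX-1 and 0.3, 0.5 or 1.0 on placebo: 1.3/1.1 = 1.18, 1.5/1.1 = 1.36, 2.0/1.1 = 1.82.
- w = 0.2 on IFX-1 and 0.3 or 0.5 on placebo: 1.08 and 1.25.
- w = 0.3 on IFX-1 and 0.1 on placebo: 1.1/1.3 = 0.85, so the direction depends on which arm deteriorates more.
- Equal w in both arms: 1.00.

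**Masking.** If IFX-1 truly had 1.18 times as many distinct infections, with w = 0.1 on IFX-1 and 0.3 on placebo, the IFX-1 to placebo ratio of record counts would be 1.18 × 1.1/1.3 = 1.00. The excess would not show in the AESI total.

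**The case against.** The strongest reply is that a record is not an event. Section 9.1.1 itself speaks of several reports of one event, and Section 10.2.3.4 counts TEAEs, so a count of distinct events is consistent with both. Section 10.2.3 calls itself a summary and leaves exact definitions to a SAP, and no Phase III counting rule, for or against, is in the available text. This stands: a reader might infer that the plan prescribes multiple counting, but the documents only leave the unit undefined. It does not remove the point, because without a link the data cannot be counted any other way.

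The totals are also descriptive. No test, alpha or stopping rule depends on them, and the patient-level figures planned beside them are not changed by extra records. That stands and limits the importance.

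A reader might further infer that entering SAEs in the AE section counts them twice. The documents do not support this. Section 9 records seriousness as an attribute of the event, Section 9.2.1 describes a second reporting channel rather than a second TEAE, and Section 9.2.1.1 keeps a change within the same SAE. Only records that are themselves serious can add to the serious total.

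Finally, the size is assumed. A reader might conclude that the totals simply repeat the mortality result, but the table produces that pattern by giving survivors no extra records, although their events can worsen too. The upper end, 1.31, needs only one distinct event per patient, which is unlikely in ventilated patients. Sections 9 and Appendix 3 narrow what is reportable in the ICU, so some early steps may never be recorded. The safety set is treated patients, so it need not be exactly 180 per arm.

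**Conclusion.** The point holds as a conditional one. If totals are taken from records, one escalating episode counts more than once, and the totals of TEAEs, serious TEAEs and AESIs shift towards the arm with more worsening. With equal distinct events, the placebo to IFX-1 ratio is about 1.03 to 1.31 under the death-based assumptions. It would be larger or smaller under other worsening rates, and the documents contain nothing to choose between them. The AESI comparison is where the shift is most likely to mislead.

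Patient counts and percentages, the tables by maximum severity or relationship, efficacy and type I error are untouched. A reader might infer that the safety comparison as a whole is compromised; the unaffected patient-level figures rule that out. This is a worthwhile, inexpensive improvement to a descriptive analysis.

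**What to change.** Keep the separate records, since they document the course of an event. Then:

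1. Link the records of one episode with a common event number on the eCRF, or by programming on preferred term and contiguous dates.
2. State in Section 10.2.3.4, the synopsis and the SAP that the total numbers of TEAEs, serious TEAEs and AESIs count each linked episode once, at its maximum severity, seriousness and relationship.
3. Show record counts separately if they are wanted, labelled as such.

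The rule should be fixed before unblinding, when Section 10.2.3 requires the SAP to be final. The cost is one field or one programming step, plus one sentence. The downside is some judgement about what forms one episode, for example when the preferred term changes along a course or an event resolves and returns. That judgement should be made blind to treatment arm.
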